data will trigger automatic alerts to clinicians who will contact those subjects for assessment. Subjects will have quarterly consultations with specialists to discuss their treatment and to collect adverse events, until the end of the 3 years of treatment. On each 3 monthly follow up, an updated medical history will be taken, alongside information on current standard of care treatment and a review of the CBMP prescribed will be undertaken (see figure 1).

Under the supervision of an appropriately qualified and trained physician, all subjects will be prescribed a dose of CBMP product that is appropriate for their type of chronic non-cancer pain, their medical history and their previous experience with cannabis. Cannabis tolerance will be monitored via ePRO data collection with tolerability questions asked after each vapourisation session. After 1 month of treatment at the low dose, this information will be used, alongside regular monitoring of the subject, to guide the Investigator on whether the subject can be titrated to the higher dose. The length of the trial for each participant is 3 years. Treatment will continue until the end of the study (see figure 1). An overview on the study procedures is given in the schedule of assessments (Table 1-1).

Figure 1; schematic of patient journey

Stage 4	
Clinic treatment phase
 
Predominantly application-based data collection, video consultation/face-to-face reviews at 3-month timepoints. Review tolerability, treatment effects and concomitant changes to standard of care
 
Patients asked if they want to join CANPAIN study and are provided with PIS about study and draft study consent form.
 
If they want to enter study inclusion/exclusion criteria confirmed and meeting arranged to review study consent form and get it signed.
 
Study protocol followed for this patient from this point on until end of maximum of 3 years

---------	--

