6.4.8 Study Treatment Discontinuation

The primary reason for study treatment discontinuation will be documented as extensively as possible. Subjects who discontinue study treatment prematurely will be followed-up until the end of study, or until they withdraw consent.

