6.6.1 Assessments during the study

- **Initiation visit/call (Day 0)**

Day 0 (baseline) for each subject will be the initial clinic visit when treatment is started. Alongside the daily monitoring of CBMP tolerability through the patient reported outcomes,

subjects will have 3 monthly consultations..

- Complete medical questionnaire form
- Review of medical history and relevant investigations
- Review current treatment being received or proposed
- Assess inclusion and exclusion criteria
- Written informed consent obtained
- Discuss the medicinal cannabis therapy
- Go through dosing instructions with participants (i.e., how to use the device, when to use the CBMP and how to enter data onto their smart device).
- If appropriate arrange the prescription

Daily assessments (concomitant with dosing)

- Tolerability NRS measurements (anxiety, drowsiness, dizziness, shortness of breath)

The tolerability measures collected 30 minutes after dosing with the CBMP are collected and fed back to Heydoc. Any NRS score >5 causes an alert, which triggers a study physician to contact the subject to assess their status and to elicit an appropriate response.

Weekly assessments

- Efficacy NRS measurements (pain, well-being, sleep quality, fatigue, nausea, depression, appetite)
- Global impression of change

3 monthly assessments

- Quality of life (SF-12)

3 monthly visits/call

- Review of efficacy and tolerability of medicinal cannabis and establishing the subject's overall impression on how they have responded to the CBMP
- Review current treatment being received or proposed
- Adverse events
- Renew prescriptions. Remind the participants of dosing instructions

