9.5 Methods of analysis

9.5.1 Effectiveness

The ITT Population will be used for all effectiveness analyses. Selected analyses may also be performed using the PP population. Effectiveness analyses will be presented for the overall populations and by subgroup of subjects (e.g. cause of chronic pain), as appropriate.

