9.5.1.1 Change in baseline pain NRS

The change in baseline pain NRS will be defined as the difference between chronic pain state at the beginning of the study versus the end of the study (after 3 years of treatment).

The primary analysis will be a difference analysis with comparison to appropriately selected matched controls. The endpoint will be tested using a two-sided z-test test to compare results between the prospectively enrolled treated participants and external matched controls. The impact of confounding factors will be reduced as much as possible by including values of important covariates in the model and by performing sub-analyses. Covariates included in the model will be selected based on:

- (1) Base line pain scores
- (2) Cannabis consumption experience and/or
- (3) Cause of chronic pain

A propensity score analysis may also be performed to match subjects between the treated and matched control groups. The propensity score is the probability of treatment assignment conditional on observed baseline characteristics. Propensity score matching entails forming

matched sets of treated and untreated participants who share a similar value of the propensity score (Rosenbaum PR & Rubin DB, 1983a and 1985).

Secondary measure outcome variables

Descriptive statistics will be presented for Quality of life changes, sleep NRS changes, Anxiety changes, confusion changes, dizziness changes, and changes in the use of concomitant medicines. Change from baseline to a number of analysis time points (including 12 months) will be assessed. Repeated measures analyses will be undertaken to allow for the evaluation of outcomes at any timepoint. In addition, multi-state modelling (MSM) will be undertaken to assess time-varying confounds. These will be described in detail in the SAP.

A comparison between treated subjects and matched control may be performed if similar endpoints are collected in both databases. Time to event analysis, multiple regression analysis for continuous and/or categorical outputs and/or propensity score analysis may be performed as appropriate.

To deal with missing data in subjects over the 3 year period, patterns of missingness will be evaluated including missing completely at random (MCAR), missing at random (MAR) or missing not at random (MNAR) will be assessed, this will be described in detail in the SAP.

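### Anxiety and dizziness change is planned at fixed times including 12 months under an ITT heading, but these scales are scheduled only after a dose, so the summary covers only patients still dosing

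*Protocol*

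**What the plan says.** All references are to the draft CANPAIN protocol in Appendix 1 unless stated otherwise.

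- **What is analysed.** Section 9.5.1.1, under secondary outcome variables, plans descriptive statistics for a list that includes "Anxiety changes, confusion changes, dizziness changes, and changes in the use of concomitant medicines". It continues: "Change from baseline to a number of analysis time points (including 12 months) will be assessed". Repeated-measures analyses are also planned.
- **In whom.** The parent section 9.5.1 states: "The ITT Population will be used for all effectiveness analyses". Section 9.3 describes ITT as using data whether or not the regimen was followed.
- **When the scales are answered.** Section 6.6.1 has a heading "Daily assessments (concomitant with dosing") and under it one item: "Tolerability NRS measurements (anxiety, drowsiness, dizziness, shortness of breath"). It then says: "The tolerability measures collected 30 minutes after dosing with the CBMP are collected and fed back to Heydoc". Section 6.1 gives the same trigger: "Cannabis tolerance will be monitored via ePRO data collection with tolerability questions asked after each vapourisation session". The clinical pathway in section 2 of the feasibility protocol also has safety questions after each inhalation session.
- **What is collected without a dose.** The weekly list in 6.6.1 covers pain, well-being, sleep quality, fatigue, nausea, depression and appetite, plus global impression of change. Anxiety and dizziness are not in it. The 3-monthly visit has a tolerability review and adverse events but names no rating scale.
- **After stopping.** Section 6.4.8: "Subjects who discontinue study treatment prematurely will be followed-up until the end of study, or until they withdraw consent".

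**The concern.** The analysis section names a fixed time and a population that includes patients who have stopped. The collection section makes the score depend on having just inhaled a dose. The first reason listed in 6.4.4 for stopping study drug is an adverse event or drug reaction that precludes further dosing. A score above 5 triggers physician contact under 6.6.1. The patients most likely to lose their later scores are therefore plausibly those with the worst ones.

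At stake is how the 12-month figure is read. Presented as an ITT change, it looks like the experience of everyone who started. It would in fact describe those who tolerated the product well enough to continue, and a lower mean at later times could be taken for habituation. The SAP can choose a missing-data method, but it cannot recover scores that the protocol never schedules.

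**Working it through.** **1. Collection against analysis.**

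| Element | Where | Dizziness | Anxiety |
|---|---|---|---|
| Change at times including 12 months | 9.5.1.1 | yes | yes |
| Also an effectiveness measure | 6.7.1 | no | yes |
| Scheduled after a dose | 6.6.1 | yes | yes |
| In the weekly list | 6.6.1 | no | no |
| Pre-dose baseline score named | 6.6.1, Table 1-1 | no | no |
| Score after stopping named | 6.4.8, 6.6.1 | no | no |

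Table 1-1 has an intolerance red-flags row, marked for daily collection and 3-monthly visits but not for baseline. It also has an overall efficacy and tolerability row, marked weekly and at 3-monthly visits. Neither row is said to be the rating scale.

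**2. Any figure in the protocol?** None for this point. The only loss allowance is in 9.2: 10% non-evaluable and 20% match failure, where 3600 / (0.9 × 0.8) = 5000. That is not a rate of stopping for intolerance, so everything below is assumed.

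**3. Direction, with no patient's score changing.** Let s be the share intolerant (scoring hi), q the share of these who stop, and r the share of the others (scoring lo) who stop.

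- Mean before stopping = s·hi + (1−s)·lo
- Mean at 12 months = [s(1−q)·hi + (1−s)(1−r)·lo] / [s(1−q) + (1−s)(1−r)]

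Take hi = 6, lo = 1.5, s = 0.10, q = 0.80, r = 0.10:

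- Before: 0.10×6 + 0.90×1.5 = 1.95
- At 12 months: (0.02×6 + 0.81×1.5) / (0.02 + 0.81) = 1.335/0.83 = 1.61
- Difference: −0.34. The share above 5 falls from 10% to 0.02/0.83 = 2.4%.

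Over s = 5–20%, q = 50–100% and r = 0–30%, the difference runs from −0.06 to −0.90. It is negative whenever q > r.

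A simpler case has all stoppers at 6 and all continuers at 2. With 10%, 20% or 30% stopping, the mean goes from 2.4, 2.8 or 3.2 to 2.0, a fall of 0.4, 0.8 or 1.2. With stoppers at 5 the fall is 0.3, 0.6 or 0.9.

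**4. Does this carry over to change from baseline?** It depends on the baseline, which is not defined for these scales.

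- If baseline is an earlier post-dose score, each continuer's change in these examples is 0, so the mean observed change at 12 months is 0 at every stopping rate.
- If baseline is a pre-dose score B (assumed equal for all), the first example gives a mean change of 1.95 − B early and 1.61 − B at 12 months. The drift between times is again −0.34, whatever B is.

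**5. Would a repeated-measures model remove it?** Largely, in a favourable case. A simulation used 30% stopping, scores of 6 against 2, residual SD 1, two scores before stopping and a random intercept. The difference fell from about −1.2 in raw means to about −0.2. What the model then estimates is scores under continued dosing, which is not the ITT description in 9.3.

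**The case against.** The strongest reply has four parts.

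- **The size is not that of the planned measure.** Section 6.2 says all analyses use changes from baseline, and step 4 shows that raw-mean differences need not carry over. This stands. A reader might infer that a bias of 0.4 to 1.2 points is expected in the planned change. The document does not support that: the figures rest on assumed scores and stopping rates and compare means over different sets of patients.
- **Safeguards exist.** The synopsis lists these scales under safety and tolerability. Section 9.5.2 uses the safety set, and 9.5.2.1 tabulates adverse events leading to discontinuation. Sections 6.4.6 and 6.4.8 record reasons for stopping. Section 9.1 promises numbers of participants and a flowchart with withdrawals from treatment. This also stands. A reader might infer that intolerance would vanish from the report, but it would not. The separate tables nevertheless do not correct a 12-month mean presented as ITT.
- **Dose-only collection is less certain for anxiety.** Anxiety is also an effectiveness measure in 6.7.1, and its absence from the weekly list may be an inconsistency. That is fair, and dizziness is the clear case.
- **Missing data are left to the SAP, and repeated measures use earlier scores.** Both are true, and scores before stopping do remain. But the protocol itself fixes the trigger, the time point and the population. Scores under continued dosing are a coherent target for a post-dose scale, provided they are not called ITT.

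The stakes are modest: a descriptive secondary summary in an exploratory draft, outside the three-month feasibility objectives. The feasibility study is, however, meant to support resubmission of CANPAIN, so the wording can still be changed.

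**Conclusion.** The point holds in a limited form. As scheduled, the anxiety and dizziness scales give no score after a patient stops CBMP, so their 12-month summary describes patients still dosing although 9.5.1 places it under ITT. For these scales change from baseline also lacks a named pre-dose baseline. If intolerant patients stop more often than others, observed-case means move toward better tolerability between time points with no change in any patient.

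That direction rests on the differential stopping, which is plausible but not stated in the protocol. The size cannot be derived. The 0.06 to 0.90 points are a range over assumed inputs for raw means, the within-patient change may be zero depending on the baseline used, and a repeated-measures model would reduce the drift. The conclusion is firm for dizziness and weaker for anxiety. It concerns the rating-scale summaries only, not the adverse-event reporting.

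**What to change.** In 9.5.1.1 and 9.5.2:

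1. Analyse the post-dose scales in the safety set.
2. Label any mean by time point as describing patients still dosing, give the number contributing, and do not call it ITT.
3. Add, for all dosed patients, the cumulative proportion with a post-dose score above 5 (the protocol's own alert level) or stopping CBMP for intolerance, whichever comes first.
4. Show the two components of that composite separately, because it mixes transient high scores with stopping.

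The cost is a small amount of extra analysis and a change of wording. Scores, alerts and reasons for stopping are already recorded, so no new collection is needed. If the sponsor wants a true ITT change in these scales, analysis wording will not deliver it. The scales would then have to be collected on calendar dates, at baseline and after stopping as well, which is a larger change to the schedule.

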6.6.2 Additional (safety) examinations

If the subject has a history of mild to moderate psychiatric ill-health that could indicate a potential sensitivity to a CBMP that subject will be referred to a specialist psychiatrist for psychiatric evaluation to further assess the risk of receiving a CBMP. In addition, if there are any unclear chronic pain related symptoms or observations the responsible physician in charge may perform further medical examinations, other than outlined in this protocol, including further clinical laboratory tests, in order to clarify the relevance or to diagnose symptoms.

6.7 Effectiveness, tolerability and safety measurements

6.7.1 Effectiveness measurements

Change from baseline in pain intensity (pain NRS).

Change from baseline in quality of life measure (SF-12)

Change from baseline in well-being (well-being NRS)

Change from baseline in fatigue (fatigue NRS)

Change from baseline in nausea (nausea NRS)

Change from baseline in depression (depression NRS)
Change from baseline in anxiety (anxiety NRS)
Change from baseline in appetite (appetite NRS)
Change from baseline in sleep quality (sleep NRS)
Change from baseline in use of concomitant pain medications
Patient's global impression of change (PGIC)

Generally, these quarterly reports compare the results to the previous quarterly results and the Specialist can make comments about the changes from the previous period.

Numerical data will be collated and reports made on the baseline changes for pain, QoL, well-being, fatigue, nausea, depression, appetite, sleep quality, anxiety, global impression of change and concomitant medication, to define whether the subject has received benefit.

6.7.2 Safety and tolerability measurements

Safety endpoints will include the following:

- Assessment of AEs, including SAEs
- Safety clinical laboratory tests

6.7.2.1 Adverse Events

Definitions and instructions for AE monitoring and reporting, are provided in Section 7.

All AEs will be coded using the version of Medical Dictionary for Regulatory Activities (MedDRA).

Safety laboratory tests

A copy of all the diagnostic and laboratory reports arranged for by the participant's Health Care Professional will be obtained at or around the time of initial visit/call and for each quarterly visit. If any adverse results are seen, the subject will either not be permitted into the study or will be asked to stop taking the CBMP at the time of a quarterly review.

7. Adverse events

7.1 Definitions

An **adverse event** is any untoward medical occurrence in a participant who has been administered a cannabis product and which does not necessarily have a causal relationship with this treatment. An adverse event (AE) can therefore be any unfavourable and unintended sign (including an abnormal laboratory finding), symptom, or disease temporally associated with the use of a medicinal product, whether related to the medicinal product.

Adverse events will be graded with respect to intensity and classified as either serious or non-serious according to the World Health Organisation classification.

Classification of adverse events

Intensity	Mild	Some awareness of symptoms, but easily tolerated.
	Moderate	Symptoms causing enough discomfort to interfere with usual activity.
	Severe	Incapacitating event causing inability to work or to perform usual activity.
Seriousness	Serious	Any untoward medical occurrence that at any dose: 
 - results in death - is life-threatening - requires participant hospitalisation or prolongation of existing hospitalisation - results in persistent or significant disability/incapacity - is a congenital anomaly / birth defect - is an important medical event.
	Non-serious:	Any other adverse event.

Note: The term "life-threatening" implies only the fact that the participant was at immediate risk of death. The term "life-threatening" does not imply a possible future course which might or might not have happened but was prevented due to adequate physician's action. For example: A simple bacterial wound infection can lead to gangrene, sepsis and eventually to death; while sepsis is usually regarded as a Serious Adverse Event because of the known high mortality, the primary wound infection itself is usually not regarded as a Serious Adverse Event. In analogy, a newly diagnosed malignant disease is usually regarded as a Serious Adverse Event because malignant diseases usually have a high mortality rate and are, therefore, life-threatening.

Hospitalisation is usually defined as an overnight stay, i.e. admission prior to midnight and continuing into the following day. A visit to an out-patient facility or Emergency Department is not necessarily a hospitalisation, although the event leading to the visit could be an SAE. Hospitalisation for elective treatment of a pre-existing condition that did not worsen during the study is not considered a Serious Adverse Event unless a complication occurs during the hospitalisation.

Adverse Event Causality

The drug regimen -event relationship will be assessed using the following criteria:

Certain: A clinical event, including laboratory test abnormality occurring in a plausible time relationship to drug administration, and which cannot be explained by concurrent disease or other drugs or chemicals. The response to withdrawal of the drug (dechallenge) should be clinically

plausible. The event must be definitive pharmacologically or phenomenologically, using a satisfactory rechallenge procedure if necessary.

Probable /likely: A clinical event, including laboratory test abnormality, with a reasonable time sequence to administration of the drug, unlikely to be attributed to concurrent disease or other drugs or chemicals, and which follows a clinically reasonable response on withdrawal (dechallenge). Rechallenge information is not required to fulfil this definition.

Possible: A clinical event, including laboratory test abnormality, with a reasonable time sequence to administration of the drug, but which could also be explained by concurrent disease or other drugs or chemicals. Information on drug withdrawal may be lacking or unclear.

Unlikely: A clinical event, including laboratory test abnormality, with a temporal relationship to drug administration which makes a causal relationship improbable, and in which other drugs, chemicals or underlying disease provide plausible explanations.

Not assessable/unclassifiable: A report suggesting an adverse reaction, which cannot be judged because information is insufficient or contradictory, and which cannot be supplemented or verified.

Unrelated: A clinical event that is judged to be clearly and incontrovertibly due to extraneous causes (disease, environment, etc.) and meet the following criteria:

- The AE does not have a reasonable temporal relationship and can be explained by a commonly occurring alternative aetiology, or
- The AE is unrelated to the study e.g. automobile accident - unless it can be demonstrated that the treatment could have caused the event.

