There is evidence that medicinal cannabis reduces the consumption of opioids in countries where medicinal cannabis has been legalized (Bradford et al., 2018). Medicinal cannabis is now being proposed as a treatment or adjunct to the treatment of opioid use disorder (OUD) (Wiese and Wilson-Poe, 2018). There is a growing evidence base that suggests a potentially de-risking strategy for medicinal cannabis in OUD.

Importantly there is extensive safety evidence for the THC and CBD balanced cannabis based pharmaceutical product from nabiximols (Sativex) although this product is not full spectrum. During its development nabiximols was found to have an excellent safety profile with regards to the development of potential THC induced adverse events such as anxiety as well as generally.

These findings provide further support to our risk mitigation strategy of providing a balanced THC and CBD medicinal cannabis product to the participants in our study.

Acute use of THC at higher doses can potentially cause reflex tachycardia in response to changes in blood pressure, with higher doses causing orthostatic hypotension and syncope. However, chronic users may develop bradycardia. (Handbook on Cannabis 2015). Cannabis can cause an acute increase in blood pressure, increasing the risk of angina (Goyal et al 2017) and it has been reported that cannabis can rarely trigger acute myocardial infarction (Mittleman et al 2001). However, in patients who have had a myocardial infarction, an 18-year follow up study showed no conclusive evidence that smoking marijuana increased mortality (Goyal et al 2017).

There is some evidence that THC has an association with road traffic accidents, and the strongest association exists with fatal road traffic accidents (Bondallaz et al., 2016). As a result, care must be taken with using medical cannabis particularly with high THC strains. As we are studying a balanced THC/CBD strain it is likely that our subject's risk will be diminished but the risk must be considered and appropriate warnings that comply with current Driver and Vehicle Licensing Agency (DVLA) guidance will be provided.

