There is literature that suggests there is a genetic risk to a patient's response to THC. To assess these genetic risks to subjects enrolling on the study we will carry out a genetic test prior to subjects receiving a CBMP using the Illumina "Genome Wide" chip to analyse an individual's genetic variance in association with cannabis tolerance and risk of cannabis use disorders (CUD). This information will be used to study the genetic risks of acute THC induced anxiety. This will involve cross validating observed patient reported outcomes related to anxiety and reported clinical anxiety adverse events, to the selected SNPs we have predicted to determine a subject's sensitivity to THC.

Conclusion

There is a long history of use of medicinal cannabis and evidence supports the concept that cannabis is generally well tolerated (especially when compared with current agents routinely used to treat chronic pain). Recently, THC levels have increased substantially for cannabis strains used recreationally which has raised concerns for the UK population in relation to addiction and the development of psychosis. Consuming a balanced THC and CBD medicinal cannabis product is known to substantially lower this risk, whilst having a full-spectrum cannabis product including minor cannabinoids and terpenes is thought to maximise the benefits to the chronic pain patient.

The full-spectrum, 8% THC/8% CBD cannabis product which will be prescribed in this study has the optimum risk benefit profile. Additionally, there could be a beneficial effect for medicinal cannabis in opioid use disorder (OUD). There is evidence of cardiovascular effects associated with THC and care must be taken with patients prone to syncope, links, although uncommon and unproven, with myocardial infarction require consideration. There is an association with road traffic accidents although the THC/CBD balanced product proposed for this study is likely to minimise this risk.

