9.5.2.1 Adverse events

Adverse events will be summarized according to the Medical Dictionary for Regulatory Activities (MedDRA) system organ class (SOC) and preferred term (PT). Any "higher-than-expected" event frequency will be investigated.

The number and percentage of subjects reporting each PT and SOC will be tabulated. A subject experiencing the same AE multiple times will only be counted once for the corresponding PT. Similarly, if a subject experiences multiple AEs within the same SOC, the individual will be counted only once for that SOC.

Similar tables will be presented for treatment-related AEs, Serious Adverse Events (SAEs), treatment related SAEs and AEs leading to discontinuation of study regimen. AEs that are reported as "possibly", "probably/likely" or "certainly" related to combination of study medication will be considered treatment related. AEs may also be summarized by highest severity and relationship to treatment. AEs will be listed for each subject.

Subject Death reported during the study will be summarized.

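### The causality scale uses a car accident as its model unrelated event although the risk section links THC to road accidents, so the treatment-related tables may under-count them

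*Protocol*

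**What the plan says.** All the text at issue is in the draft CANPAIN protocol in Appendix 1, except where stated.

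- **Risk section (4.2.1).** "There is some evidence that THC has an association with road traffic accidents, and the strongest association exists with fatal road traffic accidents". For the balanced product, "it is likely that our subject's risk will be diminished but the risk must be considered". The conclusion of the section repeats the point: "There is an association with road traffic accidents although the THC/CBD balanced product proposed for this study is likely to minimise this risk".
- **Causality scale (7.1), Unrelated.** The lead-in is "A clinical event that is judged to be clearly and incontrovertibly due to extraneous causes (disease, environment, etc.) and meet the following criteria". Two criteria follow, joined by *or*. The first needs both the absence of a reasonable temporal relationship and a common alternative aetiology. The second is "The AE is unrelated to the study e.g. automobile accident - unless it can be demonstrated that the treatment could have caused the event".
- **Causality scale (7.1), Possible.** This covers an event "with a reasonable time sequence to administration of the drug, but which could also be explained by concurrent disease or other drugs or chemicals".
- **Tables (9.5.2.1).** Events scored possibly, probably/likely or certainly "related to combination of study medication will be considered treatment related". All AEs are also tabulated by preferred term and system organ class, SAEs have their own tables, AEs are listed by subject, and deaths are summarised.
- **Actions (6.4.6).** After a withdrawal for an AE, the report to the regulator depends on whether the sponsor's clinician attributes the event to study medication. The provision for stopping the trial after an SAE applies when the event is judged at least possibly related.

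**The concern.** The scale takes as its standard example of a non-drug event one that the risk section links to the drug. It also sets a different evidential test for that event. Possible needs only plausible timing and tolerates a competing explanation, while the car-accident criterion keeps the event Unrelated until something is demonstrated. Two assessors with the same crash record could choose different categories, and each could cite the text.

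At stake is whether one of the harms that the protocol itself names is fully visible in the treatment-related AE and SAE tables, and whether the relatedness-dependent steps in section 6.4.6 are triggered for it. The label carries extra weight because the design is single-arm. Section 6.2 takes no tolerability data from the matched controls, and the synopsis groups adverse events with safety and tolerability, so an all-causality accident count would probably have no control rate beside it.

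**Working it through.** No arithmetic applies: the plan states no figure on this point. The check sets the passages side by side.

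**1. What the second criterion adds.** Without its example and exception, it says only that an event is unrelated if it is unrelated. The working content is therefore the car accident and the demonstration clause. Because the criteria are joined by *or*, this one applies without the timing test in the first.

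**2. What limits it.** The lead-in governs both criteria, so the cause must first be judged plainly external. The exception asks only that treatment *could have* caused the event, not that it did.

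**3. Three hypothetical records put through the text.**

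| Record | Reading the car-accident example | Reading the whole scale |
|---|---|---|
| (a) Participant driving, crash 40 minutes after a session, no toxicology | Unrelated: nothing has been demonstrated | Possible is open: section 4.1 gives activity of up to 1 hour, so the timing is reasonable, and the lead-in is not met |
| (b) Participant driving, crash the morning after an evening session, drowsiness reported | Unrelated, for the same reason | Possible is arguable: the interval exceeds that hour, but a reported symptom links treatment and event |
| (c) Participant in a stationary car struck by another vehicle | Unrelated | Unrelated through the lead-in |

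The competing explanations listed under Possible are concurrent disease, other drugs or chemicals. They fit this population, whose members may be taking opioids or other analgesics as standard of care. Records (a) and (b) show the inconsistency: the example points one way and the rest of the scale allows or favours the other.

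**4. Where the label goes.** An event scored Unrelated is absent from the treatment-related AE and treatment-related SAE tables (9.5.2.1) and does not meet the relatedness conditions in section 6.4.6. It stays in the tables of all AEs and all SAEs, the subject listings and, if fatal, the death summary. Section 7.2 has participants report events whatever they think the cause was. Section 7.3, as worded, makes any unexpected SAE a SUSAR without a causality condition.

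**5. Size.** The number of under-counted events would need an accident rate, a relative risk on treatment, the follow-up time and the share of crashes that assessors label Unrelated because of the example. The document gives no accident rate, no relative risk and no such share.

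**The case against.** The strongest answer is that section 7.1, read in full, already protects against the problem. Unrelated needs a clear and incontrovertible external cause, the exception needs only plausibility, and section 4.2.1 supplies that plausibility for any crash in a participant who was driving. A careful assessor would score record (a) as Possible. Nor is any event lost, because the all-causality outputs keep it and section 9.5.2.1 says that event frequencies above expectation will be investigated.

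Most of this stands, and it limits the point. A reader might infer that every car accident is Unrelated by default, that positive proof of causation is needed to change this, and that the treatment-related tables would therefore miss such events. The lead-in and the words *could have* do not support that reading. A reader might also want to multiply an outside accident rate by the planned 5000 participants and 3 years. The result would rest wholly on figures that the document does not contain.

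What does not stand is the idea that the lead-in resolves the conflict. A named example is what an assessor is likely to reach for, and this one points away from the lead-in and from the risk section. The all-causality tables also do not repair the relatedness-dependent steps in section 6.4.6.

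On scope, the rule belongs to a draft that received a non-acceptance opinion, and section 3.1 of the feasibility protocol counts patients with safety issues without a causality split. The feasibility count is therefore unaffected. The feasibility study is meant to support resubmission of CANPAIN, however, so the draft can be corrected before then.

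**Conclusion.** The inconsistency between sections 4.2.1 and 7.1 of Appendix 1 is real. Its effect is a possible under-count of road accidents in the treatment-related AE and SAE tables and in the actions tied to relatedness. It is not a certain omission or a loss of the events from the record. The size cannot be derived from the document. The conclusion assumes that at least some assessors will be guided by the named example rather than by the lead-in. If all of them apply the lead-in and the exception strictly, the effect is small. The wording should still be reconciled, because the event concerned is one that the protocol says must be considered and the correction is cheap.

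**What to change.** 1. **Section 7.1.** Delete the car-accident example and the demonstration clause, so that road accidents are judged on the ordinary causality scale and agree with section 4.2.1. Reword what remains of the second criterion, which would otherwise be circular. It should admit events that a clear and incontrovertible external cause fully accounts for, whatever their timing, such as a stationary participant struck by another vehicle. Keeping only the first criterion would go too far: it requires the absence of a reasonable temporal relationship, so a plainly external crash soon after a session could no longer be scored Unrelated.
2. **Section 9.5.2.1.** Add a table of all road traffic accidents regardless of causality.

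The cost is an edit to one criterion and one extra table. Treatment-related counts may come out slightly higher. Nothing in the feasibility study's own objectives needs to change.
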